We propose a model (Figure 1) based on this premise that makes testable predictions about the interaction of the CV with chronic and acute MA administration in MUD. Our preliminary data show that the CV causes overexpression of TAAR1 in cell culture. Stimulation of the TAAR1 receptor decreases dopaminergic signaling in mesocorticolimbic and corticostriatal networks (Pei et al., 2016;Berry et al., 2017). We propose that this effect in conjunction with chronic MA use causes neuroadaptations that result in the increased striato- and corticolimbic RSFC as well as increased drug craving observed in MUD subjects with the CV. We can indirectly test the hypothesis of decreased DA release due to ever-expression via MA administration. The effect of acute MA administration on RSFC in humans is not known but acute administration of S-amphetamine

(Schrantee et al., 2016) and methylphenidate (Konova et al., 2013) reduce RSFC in salience attribution and default mode networks presumably via increased DA release. Stimulation of over-expressed TAAR1 should blunt this effect in CV carrying individuals compared to WT. There are no published reports on neural effects of the interaction between either chronic or acute MA administration and *htaar1* genotype in humans, therefore this proposal represents a unique opportunity to determine whether the RSFC response to acute MA administration in humans is mediated by genotype.

In Specific Aim 1 (SA 1), we will confirm and extend our preliminary RSFC findings in *chronic* MUD using seed-based and data-driven precision brain mapping approaches. The latter are made possible by extended (40 minute) acquisition of functional connectivity data. We will investigate genotype and drug x genotype interactions with full connectivity matrices as well as topological RSFC measures including connection density and strength, network segregation, global efficiency, rich club coefficients, and global segregation in MA users at baseline and after MA administration. In SA 2, we will examine how htaar1 genotype modifies the effects of acute MA administration on neural and behavioral measures in MUD. This provides an indirect test of Figure 1A that genotype modifies TAAR1 expression in the ventral tegmental area (VTA) and thus DA release in the striatum.

SA 1. Determine the influence of *htaar1* CV vs. wild type (WT) genotype on RSFC and craving in *chronic* MUD.

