Research Match and OHSU OCTRI Research Volunteer Registry will be used to recruit potential subjects. An IRB approved description of the study will be sent to individuals by Research Match who meet criteria for the study. If the individual indicates they are interested, their contact information (i.e. name, mailing address, email, phone number) will be sent through Research Match to the [name] Lab Research Match account. This information will remain in the ResearchMatch system and/or be exported to the OHSU RDS server. OHSU OCTRI Research Volunteer Registry will provide contact information of individuals who meet study criteria and this information with be stored on the OHSU RDS server. Research assistants will contact these individuals using phone or email to set-up a phone screen. Subjects will be emailed via [contact] to set up a phone screen. The [name] lab has substantial capacity and expertise to recruit MUD participants. Per NIDA guidelines, MUD subjects who have been referred to appropriate VA or community treatment facilities but will not be in drug treatment (court-mandated or otherwise) when recruited or while participating in the study (if subjects choose to join a treatment program during their participation in the study they will be withdrawn from the study and will not be administered methamphetamine). The community assistance programs we work with interact with precontemplative methamphetamine users regularly. Subjects may also be recruited by calling participants who previously consented to being contacted for future research after enrollment into the MARC study (eIRB 8702). As the IRB previously approved, these subjects will be pulled directly from the MARC study, not from a contact information repository. CPRS will not be accessed for screening purposes. Subjects who call in response to advertisements are screened with a telephone script to verify likelihood of meeting criteria and, if indicated, given an initial appointment. Additional questions will be asked to screen for recent exposure and symptoms of COVID-19. If recent exposure or symptoms are disclosed, and the subject otherwise qualifies, we will wait to schedule them until they have self-isolated for two weeks from time of exposure and/or when their symptoms have completely resolved. Our screening criteria already excludes those who are at increased risk of severe illness from COVID-19; however some subjects who *might* be at an increased risk may still qualify to participate during modified operations including smokers and those with wellcontrolled moderate-to-severe asthma, hypertension, and/or high blood pressure. These subjects will be informed that they may be at higher risk for COVID-19 infection and they may not want to put themselves at risk by participating in research. A VA waiver of informed consent and authorization for screening/recruitment purposes will be requested to collect subject names, phone numbers, and email before potential subjects give formal informed consent. Email addresses will be collected on the screening form for scheduling purposes and, if the potential subject agrees, email will be collected to send an appointment confirmation email (Azure). Each subject will provide written informed consent before any data collection or additional screening takes place. Up

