
to 100 current users of methamphetamine (MA) who meet DSM-V criteria for MA use disorder (MUD) and 100 controls will be recruited for this project and 36 from each group will complete all study procedures (we anticipate many will screen out based on their genetic screening for TAAR1). These 72 will break down into 4 groups of 18:

- MUD Wild Type (WT) Group: MUD individuals who are WT for the TAAR1 gene
- MUD Common Variant (CV) Group: MUD individuals who are hetero- or homozygous for the V288V SNP on the TAAR1 gene
- CS WT Group: Healthy controls who are WT for the TAAR1 gene
- CS CV Group: Healthy controls who are hetero- or homozygous for the V288V SNP of the TAAR1 gene

Data (including MRI scans) and specimens (saliva) may be pulled from the MARC Biorepository (mIRB 3164) to supplement subjects enrolled into this study for data analysis. Data and specimens will be coded and will not include any identifiers. A Waiver of Process of Informed Consent/Authorization will be obtained for analysis of these data/specimens and a DUA will be fully executed before data/specimens are removed from the repository. Repository data shared with this project may be sent to the University of Minnesota for analysis as described below in **Specific Outcome Measures and Hypotheses**. This data will be a Limited Data Set that includes imaging data (defaced), demographics such as age (no one over age 89), sex, treatment assignment (meth and placebo), TAAR1 genotype, substance use variables and survey scores. Data will be shared with study team members currently approved by the VA/OHSU joint IRB for this protocol. As this data is being shared from the repository (Sender) to Minnesota under this protocol (Recipient), a DUA between the repository and University of Minnesota will be fully executed before data is removed.

Inclusion/ Exclusion criteria: Entry criteria will be assessed based on self-report questionnaires, medical history and psychiatric diagnosis. Data/specimens pulled from the MARC biorepository will have come from subjects with very similar relevant inclusion/exclusion criteria which will be evaluated before inclusion.

Criteria for Inclusion:

All groups:

- * 18 to 55 years old
- * Homozygous or heterozygous for the hTAAR1 V288V genotype or wild type for hTAAR1 (Part 2)

MUD groups:

- * Subjects must have a positive urine drug screen for methamphetamine during visit one
- * Meets current criteria for methamphetamine use disorder

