MA Metabolites: Blood/oral fluid drawn will be stored in a VAPORHCS freezer and then sent to the Center for Human Toxicology at the University of Utah to quantify the level of meth and meth metabolites present in the sample using Gas Chromatography/Mass Spectroscopy. Samples will be shipped via courier on dry ice (NIDA contract N01DA-19-8951). Samples will be recoded with a number (consecutive numbers, 1,2,3,etc) and will be labeled with this number prior to being shipped. No other information will be on the label or be provided to the University of Utah. These samples will be acquired once during V1 and twice each during V3 and V4 for individuals in the MUD group. Samples will be acquired only once during V3 and once during V4 for control subjects, after study drug is administered.

Biorepository Data/Specimen Use: A separate cohort of data/specimens will be pulled from the MARC biorepository and included in the analysis for this project. Data/specimens pulled will be nearly identical to the data used in this project and will include demographics (no identifiers), questionnaire data, information on drug/alcohol abuse, mental health diagnoses, computer task data, imaging data (MRI), coded lab results and saliva samples. Saliva samples will be sent out with the other saliva samples collected for this project and analyzed for methamphetamine metabolites at the University of Utah.

Data Acquisition and Processing

Rating scales: Subjective endpoints (MA-elicited craving, subjective high and intoxication), positive affect, will be measured using self-report surveys administered prior to scanning and again after the scan (Table 1). **MRI Acquisition:** We will use a 3T Siemens Magnetom Prisma scanner and a 32-channel phased array head coil. RSFC (T_2^* -weighted): One T_2^* - weighted echo-planar imaging (EPI) functional run will be acquired. Each run will utilize real-time motion tracking, Framewise Integrated Real-time MRI Monitoring (FIRMM), to ensure at

Instrument	Measures		
Visual Analog Scale for	Methamphetamine		
mood (VAS-today)	effects		
Visual Analog Scale for craving (VAS-crave)	Drug liking		
Addiction Research Center Inventory (ARCI)	Drug effects		
Global Rating of Stimulation (GRS)	Stimulation		
Profile of Mood States (POMS)	Active mood states		
Profile of Mood States-Bi Elevation (POMS-E)	Active mood states		
Rapid Visual Information Processing Task (RVIPT)	Sustained attention		

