PS2: TAAR1 genotype modulates RSFC in CS and MUD: Samples from the MARC Data Repository were examined under an IRB approved protocol. The *htaar1* gene was sequenced in 24 CS (15 WT and 9 CV) and 26 MUD subjects in remission (13 WT and 13 CV) by the Core Laboratory at OHSU. The reported allelic frequency of the synonymous v288v SNP in the general population is 22% (Lek et al., 2016) and, in our sample, 24%. There was no difference in the distribution of v288v genotypes between MUD and CS. Homozygotes for the CV (n=4) were combined with heterozygotes for comparison to the WT group.

RSFC scans were processed with FSL (Smith et al., 2004) using a variation on the methods in Kohno et al. (2017). We hypothesized that effects of TAAR1 genotype would be most robust in striatum. Thus, we examined RSFC between a ventral striatum (VS) seed and dorsal striatum (DS), midbrain, insula, anterior cingulate and dorsolateral prefrontal cortex and found a significant main effect of group (p = 0.018) and a group by genotype interaction (p < 0.005) with the regions in Figure 3.

PS3: Effect of CV v288v SNP on expression of TAAR1 receptor in vitro: Chinese Hamster Ovary cells

in culture were transfected with equal doses of either WT or CV cDNA tagged with Venus (a yellow fluorescing variant of green fluorescent protein). Figure 5 indicate more *protein* expression for the CV by the Venus light intensity. The Venus tag is part of the protein molecule and co-

expressed with the TAAR1 receptor. Note that at all post transfection time points, the CV protein was expressed at higher levels than the WT protein. Finally, cAMP production (Figure 5D) was higher in the CV transfected cells compared to WT transfected cells in response to beta phenethylamine, but EC50s were similar. So, it is

[figure not shown]
[figure not shown]

Figure 5: Fluorescent VENUS tagged- WT or -v288v hTAAR1 were transiently transfected into cells. Cells were collected and counted at 4, 24 and 48 hours post transfection. Fluorescence intensity was measured using a PerkinElmer Victor X light fluorescence plate reader. Light intensity was normalized to cell number of each condition (expressed as % WT) to correct for cell growth at different time points. Bar heights are mean ±SEM, * *P*<0.01. [name] and [name] (2017), private communication.

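### MARC repository subjects are pooled with new enrolees without a source term or a rule against overlap with the pilot sample or the enrolees, so the type I error of the SA 1 confirmation is not assured

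*Combined protocol and SAP*

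**What the plan says.** Two places in the combined protocol and SAP describe the pooling. Under Biorepository Data/Specimen Use: "A separate cohort of data/specimens will be pulled from the MARC biorepository and included in the analysis for this project". Under Recruitment, data and specimens "may be pulled from the MARC Biorepository (mIRB 3164) to supplement subjects enrolled into this study for data analysis". One is definite and the other optional, and neither gives a number. Repository records are coded and carry no identifiers. Their subjects come from closely similar eligibility criteria, which are to be checked before inclusion.

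Under Specific Aims and Rationale, SA 1 is framed as confirmation: "we will confirm and extend our preliminary RSFC findings". The connectivity pilot is PS2 under Preliminary Studies: "Samples from the MARC Data Repository were examined under an IRB approved protocol". Its sample was "24 CS (15 WT and 9 CV) and 26 MUD subjects in remission (13 WT and 13 CV"), and it reported a group-by-genotype interaction at p < 0.005.

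Under Specific Outcome Measures and Hypotheses, the mixed model has genotype as its single between-subjects variable. That section refers to a section 4.4 for statistical design and power, which is not in the text available.

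Recruitment adds: "Subjects may also be recruited by calling participants who previously consented to being contacted for future research after enrollment into the MARC study". Imaging from this study is itself to be banked in the MARC biorepository (Data and Safety Monitoring Plans).

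**The concern.** A test confirms a pilot finding only if its data are independent of the data that suggested the finding. Here both the pilot and the supplementary cohort come from MARC, and no rule in the text keeps PS2 subjects out of the confirmatory set.

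A second route is double counting. Earlier MARC participants may enrol here, and this study's own images go back into MARC. The same person could therefore appear once as an enrolee and once as a repository record. Analysts who receive records without identifiers cannot see this, and a model that treats the two rows as independent understates the variance.

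A third issue needs no overlap. Under Subject selection and randomization, new subjects enter in blocks of three CV and three WT. Repository subjects need not be balanced in this way. Without a source term, any mean difference between the cohorts can then enter the genotype contrast.

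**Working it through.** The text available states no alpha, power, effect size or repository number, so there is no figure of the plan's own to reproduce. I assume a two-sided 5% test, equal variances and a normal approximation.

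**Inputs from the documents**
- New completers: 18 per genotype in each of the MUD and control arms (4 × 18 = 72).
- PS2: controls 15 WT and 9 CV; MUD 13 WT and 13 CV.
- PS2 interaction: p < 0.005.

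**Assumed:** the extent of any overlap; 13 repository subjects per genotype in the double-counting check; within-person correlation 0.5 to 0.9.

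**1. No overlap.** Different people from the same repository are independent of the pilot, so the error rate stays at 5%. Simulation under the null, after a significant pilot, gives 4.9% with 18 new subjects per genotype and 5.0% with 13 other repository subjects per genotype added.

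**2. Only the 24 PS2 controls reused, group-by-genotype test.** In units of the residual variance:
- Pilot contrast variance: 1/15 + 1/9 + 2/13 = 0.3316.
- Pooled control cells: 18 + 15 = 33 WT and 18 + 9 = 27 CV. MUD cells stay at 18.
- Pooled contrast variance: 1/33 + 1/27 + 2/18 = 0.1785.
- Covariance of the two contrasts: 1/33 + 1/27 = 0.0673.
- Correlation r = 0.0673 / √(0.1785 × 0.3316) = 0.277.

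Given a pilot statistic z, the pooled statistic is normal with mean r·z and variance 1 − r². Integrating P(|Z pooled| > 1.96) over pilots that reached significance gives 9.0% if the pilot was selected at p < 0.05 and 12.9% if selected at p < 0.005.

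**3. People counted twice, MUD genotype contrast.** With 18 new and 13 repository rows per genotype (31 in all), k people appearing twice and within-person correlation ρ, the true variance exceeds the assumed variance by the factor V = 1 + 2kρ/31. The error rate is P(|Z| > 1.96/√V).

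| k per genotype | ρ = 0.5 | ρ = 0.7 | ρ = 0.9 |
|---|---|---|---|
| 0 | 5.0% | 5.0% | 5.0% |
| 3 | 6.1% | 6.6% | 7.1% |
| 6 | 7.3% | 8.2% | 9.1% |

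For example, k = 3 and ρ = 0.5 give V = 1 + 3/31 = 1.097.

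**4. Cohort difference without overlap.** If repository subjects differ from new subjects by δ on average, the CV minus WT contrast shifts by δ × [m_CV/(18 + m_CV) − m_WT/(18 + m_WT)], where m is the repository count per genotype. With a 13:13 split the shift is zero. With a split like the PS2 controls (9 CV, 15 WT, used only to illustrate imbalance) it is δ × (9/27 − 15/33) = −0.12δ. A source term removes this shift.

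**The case against.** The strongest reply is that the documents point away from reuse of PS2. They call the repository data a separate cohort, nearly identical in content to this project's data. The data set to be shared includes methamphetamine or placebo assignment, which PS2 does not describe, so an earlier dosing study is a plausible source. PS2 names a MARC Data Repository and the pooling text a MARC Biorepository, and nothing says that they are the same. SA 1 concerns genotype in chronic MUD, where controls do not enter. Records are coded, so matching is possible. Section 4.4 may say more.

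Much of this stands, and it is why overlap cannot be asserted. It does not close the gap. The text does not say what the cohort is separate from. The Recruitment wording, "to supplement subjects enrolled into this study for data analysis", suggests separate from new enrolees, not from PS2. The PS2 result to be confirmed is an interaction, and controls do enter that test. Matching is possible, but no one is assigned to do it.

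A reader might infer much larger error rates. Three such figures are not supported:
- **18% or 43%.** Pooling the 26 PS2 MUD subjects with 36 new ones, with z = √(26/62)·z_pilot + √(36/62)·N(0,1), gives 18% at z_pilot = 1.96 and 43% at 2.81. Those 26 were in remission and would not meet the active-use criteria for the MUD groups. The 2.81 also comes from an interaction across all 50 subjects, not from a MUD-only genotype test.
- **15%.** The same formula with PS1's 13 active users (z = 2.1) gives 15%, but PS1 is not said to come from MARC.

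Nor does pilot reuse reach Hy 2 or Hy 3, because no preliminary study reports a drug-by-genotype result.

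**Conclusion.** The point holds as a gap in the analysis definition, not as a demonstrated inflation. The text available does not assure the type I error of the SA 1 confirmation, because overlap is neither stated nor excluded.

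The rate is 5% with no overlap. It is about 9% to 13% if only the PS2 controls are reused and the test is group by genotype; a MUD-only genotype contrast would be untouched by that reuse. It is about 6% to 9% with 3 to 6 people per genotype counted twice, under the assumed 13 repository subjects per genotype and correlation of 0.5 to 0.9.

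Pilot reuse concerns SA 1 and Hy 1 only. Double counting and unmarked pooling can also affect Hy 2 and Hy 3.

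**What to change.** 1. Before release, the repository administrator removes by code anyone used in PS2, anyone used in PS1 if those subjects are in MARC, and anyone also enrolled under this protocol. If there is no overlap, a sentence recording that check is enough.
2. Add a data-source term to every analysis that pools repository and enrolled subjects.
3. Report the confirmatory SA 1 test in subjects enrolled under this protocol, and label the pooled result as secondary.

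The cost is one code match, one model degree of freedom, and no gain in precision from repository subjects in the confirmatory SA 1 test. The pooled secondary analysis keeps that gain.
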